## 1. SYNOPSIS

**Protocol Title:** A single centre, open label, one sequence, cross-over study to evaluate the effect of itraconazole on the pharmacokinetics of single inhaled doses of nemiralisib in healthy subjects.

**Short Title:** A study to evaluate the effect of itraconazole on the PK of nemiralisib

### Rationale:

The *in vitro* Cytochromes P450 (CYP) phenotyping study and *in vitro* inhibition data indicate CYP3A4 may be the major route of clearance for nemiralisib. Therefore, the co-administration of drug therapies which modulate CYP3A4 (specifically CYP3A4 inhibitors) may alter the exposure of nemiralisib (i.e. increase in exposure). Current recommendations by regulatory agencies Food and Drug Administration (FDA) and European Medicines Agency (EMA) specify that “*when metabolism is a significant pathway (i.e. constitutes 25% or more of the drug’s overall elimination) in vivo studies using appropriate inhibitor(s)/inducer(s) are warranted*”. In line with recommendations, this clinical drug interaction study with itraconazole (a potent CYP3A4 inhibitor) is required. Ongoing and future clinical studies using nemiralisib will use the data generated from this current study to justify inclusion / exclusion criteria based on concomitant medications which affect CYP3A4 and potentially inform dose modification in case of co-administration with medication affecting CYP3A4 activity.

### Objectives and Endpoints:

Objectives	Endpoints
Primary 
 
To characterize the effect of repeat oral dosing of itraconazole on the pharmacokinetics of a single inhaled dose of nemiralisib in healthy subjects
 
	
 
AUC(0-∞), AUC(0-t), Cmax, tmax , t1/2
 

Secondary 
 
To investigate the safety and tolerability of single inhaled dose of nemiralisib, when dosed alone and concomitantly with itraconazole, in healthy subjects
 
To investigate the pharmacokinetics of itraconazole and hydroxy-itraconazole when co-administered with nemiralisib
 
	
 
Adverse events (AE), clinical laboratory values, vital signs, electrocardiogram (ECG) and spirometry
 
AUC(0-∞), AUC(0-t), Cmax, tmax, t1/2
 

AUC(0-∞) Area under the concentration-time curve from time zero (pre-dose) extrapolated to infinite time, AUC(0-t): Area under the plasma concentration versus time curve from time zero to t, Cmax; maximum observed plasma concentration, tmax : time to Cmax, t1/2: Terminal phase half-life

**Overall Design:**

This is a Phase I, single centre, open label, one sequence cross-over study to be conducted in healthy males and females of non-child bearing potential. The study will evaluate the Pharmacokinetic (PK), safety and tolerability of nemiralisib when administered alone and when administered concomitantly with repeat doses of itraconazole, a known strong inhibitor of CYP3A4, to simulate a steady-state exposure of itraconazole.

The pharmacokinetics of itraconazole and hydroxy-itraconazole (its hydroxy-metabolite) will be assessed to provide precise estimates of its pharmacokinetics to validate and support any interaction observed with nemiralisib as well as future usage via *in silico* modelling for nemiralisib and other drugs.

**Number of Participants:**

Approximately 20 participants will be enrolled such that approximately 16 evaluable participants complete the study.

**Treatment Groups and Duration:**

Each participant will participate in the study for approximately 7 weeks. They will complete a screening visit, 2 treatment periods (nemiralisib alone followed by nemiralisib co-administered with itraconazole), and a follow up visit.

**Screening:**

Participants must be screened within 21 days before the first dose (Day 1), and must meet all eligibility criteria.

**Period 1:**

- Participants will be admitted to the clinical research unit on Day -1 and will remain in-house until collection of the final PK sample on Day 6.
- On Day 1, participants will receive a single dose of 100 mcg nemiralisib.

**Period 2:**

- There will be a washout of at least 14 days between the administration of nemiralisib in Period 1 and the administration of nemiralisib in Period 2.
- Participants will be admitted to the clinical research unit on Day -1 and will remain in-house until collection of the final PK sample on Day 11.
- From Day 1 to 10 inclusive, participants will receive a single dose of 200 mg itraconazole in the morning.
- On Day 5, participants will receive a single dose of 100 mcg nemiralisib one hour after the dose of 200 mg itraconazole.

**Follow-up:**

Participants will be instructed to return for a follow-up visit 5-10 days after the last dose of itraconazole.

## 2. SCHEDULE OF ACTIVITIES (SOA)

**Table 1** Screening and Follow-up

Procedure	Screening (up to 21 days before Day 1)	Follow-up (within 5–10 days of last dose itraconazole)	Notes
Informed consent	X		
Demography	X		
Inclusion and exclusion criteria	X		
Past and current medical conditions	X		
Medical history (includes substance usage)	X		Substances: Drugs, Alcohol, tobacco and caffeine
Physical examination	X	X	Full examination (including height and weight) at screening, brief examination at follow-up
Vital signs	X		Triuplicate
12-lead ECG	X	X	Triuplicate
FEV 1 and FVC	X		Triuplicate
Laboratory assessments (hematology and clinical chemistry)	X	X	
Urinalysis	X		
HIV, Hepatitis B and C screening	X		If test otherwise performed within 3 months prior to first dose of study treatment, testing at screening is not required
Alcohol breath test & drug screen	X		Includes urine cotinine test
SAE review	X	X	
AE review		X	

ECG: Electrocardiogram, FEV1: Forced expiratory volume in 1 second, FVC: Forced vital capacity, HIV: Human immunodeficiency virus, AE: Adverse event, SAE: Serious adverse event.

**Table 2** **Period 1**

Procedure	Treatment Period Days							Notes
	-1	1	2	3	4	5	6	
Admission	X							
Discharge							X	
Alcohol breath test & drug screen	X							Includes urine cotinine test
Laboratory assessments (hematology, clinical chemistry and urinalysis)	X						X	Day -1 results to be reviewed before dosing on Day 1
Brief physical examination	X						X	
Inhaler (Ellipta™) training	X							Training conducted by reviewing the Patient Information Leaflet with the participant. Additional training may be conducted at the discretion of the investigator.
FEV 1	X							Triuplicate.
12-lead ECG		X					X	Single measurement. Pre-dose on Day 1.
Vital signs		X					X	Single measurement. Pre-dose on Day 1.
Study treatment (nemiralisib)		X						
Pharmacokinetic (PK) (nemiralisib)		X	X	X	X	X	X	pre-dose, and 5 min, 30 min, 2 h, 6 h, 12 h, 24 h, 48 h, 72 h, 96 h and 120 h post-dose
AE review		←=====→						
SAE review	X	←=====→						
Concomitant medication review	X	←=====→						

**Table 3 Period 2**

Procedure	Treatment Period Days												Notes
	-1	1	2	3	4	5	6	7	8	9	10	11	
Admission	X												
Discharge												X	
Alcohol breath test & drug screen	X												Includes urine cotinine test
Brief physical examination	X											X	
Laboratory assessments (hematology, clinical chemistry and urinalysis)	X										X		Pre-dose at all timepoints. Day -1 results to be reviewed before dosing on Day 1.
Clinical chemistry only			X		X		X		X				Pre-dose at all timepoints. Day 4 results to be reviewed before itraconazole dosing on Day 5.
12-lead ECG		X	X		X		X		X		X		Single measurement. Pre-dose and 3h post-dose (itraconazole) on Day 1. Pre-dose at all other timepoints, Day 4 results to be reviewed before itraconazole dosing on Day 5.
Vital signs		X	X		X		X		X		X		Single measurement. Pre-dose at all timepoints
Study treatment (itraconazole)		X	X	X	X	X	X	X	X	X			Approx. 1 h post standard meal.
FEV 1					X								Triuplicate
Inhaler (Ellipta) training					X								Training conducted by reviewing the Patient Information Leaflet with the participant. Additional training may be conducted at the discretion of the investigator.
Study treatment (nemiralisib)						X							1 h post itraconazole administration.
PK (nemiralisib)						X	X	X	X	X	X	X	pre-dose, and 5 min, 30 min, 2 h, 6 h, 12 h, 24 h, 48 h, 72 h, 96 h, 120 h and 144 h post-dose (nemiralisib)

Procedure	Treatment Period Days											Notes
	-1	1	2	3	4	5	6	7	8	9	10	
PK (itraconazole + hydroxy-itraconazole)		X				X	X					Pre-dose, 30 min, 1 h, 1.5 h, 2 h, 3 h, 4 h, 6 h, 8 h, 12 h post-dose (itraconazole) on Day 1  Pre-dose, 30 min, 1 h, 1.5 h, 2 h, 3 h, 4 h, 6 h, 8 h, 12 h and 24 h hours post-dose (itraconazole) on Day 5
AE review		←=====→										
SAE review	X	←=====→										
Concomitant medication review	X	←=====→										

- The timing and number of planned study assessments, including safety and pharmacokinetic assessments may be altered during the course of the study based on newly available data (e.g., to obtain data closer to the time of peak plasma concentrations) to ensure appropriate monitoring.
- Any changes in the timing or addition of time points for any planned study assessments must be documented and approved by the relevant study team member and then archived in the sponsor and site study files, but will not constitute a protocol amendment. The Institutional review board (IRB)/ Independent ethics committee (IEC) will be informed of any safety issues that require alteration of the safety monitoring scheme or amendment of the Informed consent form (ICF).

### 3. INTRODUCTION

#### 3.1. Study Rationale

The *in vitro* CYP phenotyping study and *in vitro* inhibition data indicate CYP3A4 may be the major route of clearance for nemralisib (Investigator's Brochure [GlaxoSmithKline Document Number [2012N141231\\_08](#)]). Therefore, the co-administration of drug therapies which modulate CYP3A4 (specifically CYP3A4 inhibitors) may alter the exposure of nemralisib (i.e. increase in exposure). Current recommendations by regulatory agencies Food and Drug Administration (FDA) and European Medicines Agency (EMA) ([[EMA](#), 2012], [[FDA](#), 2017]) specify that "*when metabolism is a significant pathway (i.e. constitutes 25% or more of the drug's overall elimination) in vivo studies using appropriate inhibitor(s)/inducer(s) are warranted*". In line with recommendations, this clinical drug interaction study with itraconazole (a potent CYP3A4 inhibitor) is required. Ongoing and future clinical studies using nemralisib will use the data generated from this current study to justify inclusion / exclusion criteria based on concomitant medications which affect CYP3A4 and potentially inform dose modification in case of co-administration with medication affecting CYP3A4 activity.

#### 3.2. Background

Nemralisib (also known as GSK2269557) is a potent and highly selective inhaled phosphoinositide 3-kinase (PI3K)-delta ( $\delta$ ) inhibitor, being developed as an anti-inflammatory agent for the treatment of Chronic obstructive pulmonary disease (COPD) and other inflammatory lung disease such as asthma and bronchiectasis. PI3K $\delta$  is a member of the Class IA family of PI3Ks, that converts the membrane phospholipid phosphatidylinositol 4,5-biphosphate (PIP2) into phosphatidylinositol 3,4,5-trisphosphate (PIP3). PIP3 is a second messenger in many cellular processes including cell growth, differentiation and migration.

PI3K $\delta$  has specific roles in mediating antigen receptor and cytokine signalling in T-cells, mast cells and B-cells. PI3K $\delta$  is thought to play an important part in various epithelial responses relevant for the development of COPD, asthma and bronchiectasis. Chronic treatment with antibiotics such as macrolides is increasingly used in these conditions to prevent exacerbations. Since macrolides, and other drugs used to treat co-morbidities associated with these conditions, are CYP3A4 inhibitors it is important to ensure that co-administration of these drugs does not substantially alter systemic nemralisib levels. Hence, in this study the systemic pharmacokinetics of nemralisib will be examined with the co-administration of itraconazole, a strong CYP3A4 inhibitor.

Nemralisib has already been administered as a nebulised solution and dry powder formulation in single and repeated doses to healthy subjects and patients with asthma and COPD, and has been well tolerated across the range of doses used. A detailed description of the chemistry, pharmacology, efficacy, and safety of nemralisib is provided in the Investigator's Brochure [GlaxoSmithKline Document Number [2012N141231\\_08](#)].

### **3.3. Benefit/Risk Assessment**

More detailed information about the known and expected benefits and risks and reasonably expected adverse events of nemirisib may be found in the Investigator's Brochure [GlaxoSmithKline Document Number [2012N141231\\_08](#)].

More detailed information about the known and expected benefits and risks and reasonably expected adverse events of itraconazole may be found in the FDA label ([Itraconazole Prescribing Information](#), 2010).

### 3.3.1. Risk Assessment

Potential Risk of Clinical Significance	Summary of Data/Rationale for Risk	Mitigation Strategy
Investigational Product (IP)		
Bronchospasm	Can potentially occur with any inhaled treatment.	
All doses of study treatment will be administered in the clinical pharmacology unit in the presence of trained clinical staff.
 
Treatment with a short-acting inhaled bronchodilator will be available and administered as appropriate and determined by the Investigator. Participants will receive no more nemiralisib treatment and may be withdrawn from the study.

Mucosal irritancy	Detected in 13 week toxicology study in the dog.	Participants will be regularly monitored for AEs. No evidence of mucosal irritancy has been seen so far in clinical studies.
Itraconazole administration	
The most common Adverse Drug Reactions associated with the administration of itraconazole are:
 
 
- Upper respiratory tract infections
 
- Increased hepatic enzymes
 
- Hypoacusis
 
- Headache
 
- Abdominal pain
 
- Diarrhea
 
	
Only healthy participants will be allowed to participate in the proposed study.
 
Exclusion criteria, close monitoring of clinical parameters and adverse events will be conducted. Stopping criteria will be utilised to mitigate and assess cardiovascular and liver effects.

Potential Risk of Clinical Significance	Summary of Data/Rationale for Risk	Mitigation Strategy
	

- Nausea

- Fatigue

- Arrhythmia

- Cough

- Sore throat

- Back pain

 
Refer to the FDA label (Itraconazole Prescribing Information, 2010) for itraconazole for the full list of Adverse Drug Reactions.
	

### 3.3.2. Benefit Assessment

Healthy participants in this study will receive no direct medical benefit. They may however benefit from the thorough medical assessments they receive during the course of the study.

### 3.3.3. Overall Benefit:Risk Conclusion

It is considered acceptable to conduct this study in healthy participants, because whilst they will receive no direct medical benefit, the risks from the study treatment and procedures are minimal. The study will be conducted in a fully equipped clinical pharmacology unit with access to hospital emergency facilities.

## 4. OBJECTIVES AND ENDPOINTS

Objectives	Endpoints
Primary 
 
To characterize the effect of repeat oral dosing of itraconazole on the pharmacokinetics of a single inhaled dose of nemralisib in healthy participants
 
	
 
AUC(0-∞), AUC(0-t), Cmax, tmax , t1/2
 

Secondary 
 
To investigate the safety and tolerability of single inhaled dose of nemralisib, when dosed alone and concomitantly with itraconazole, in healthy participants
 
To investigate the pharmacokinetics of itraconazole and hydroxy-itraconazole when co-administered with nemralisib
 
	
 
Adverse events (AE), clinical laboratory values, vital signs, electrocardiogram (ECG) and spirometry
 
AUC(0-∞), AUC(0-t), Cmax, tmax, t1/2
 

AUC(0-∞) Area under the concentration-time curve from time zero (pre-dose) extrapolated to infinite time, AUC(0-t): Area under the plasma concentration versus time curve from time zero to t, Cmax; maximum observed plasma concentration, tmax : time to Cmax, t1/2: Terminal phase half-life

## 5. STUDY DESIGN

[figure not shown]
### 5.1. Overall Design

This is a Phase I, single centre, open label, one sequence cross-over study to be conducted in healthy males and females of non-child bearing potential. The study will evaluate the PK, safety and tolerability of nemralisib when administered alone and when

administered concomitantly with repeat doses of itraconazole, a known strong inhibitor of CYP3A4, to simulate a steady-state exposure of itraconazole.

The pharmacokinetics of itraconazole and hydroxy-itraconazole (its hydroxy-metabolite) will be assessed to provide precise estimates of its pharmacokinetics to validate and support any interaction observed with nemiralisib as well as future usage via *in silico* modelling for nemiralisib and other drugs.

Each participant will participate in the study for approximately 7 weeks. They will complete a screening visit, 2 treatment periods (nemiralisib alone followed by nemiralisib co-administered with itraconazole), and a follow up visit (see Figure 1).

**Figure 1** Overall study schematic

Screening:

Participants must be screened within 21 days before the first dose (Day 1), and must meet all eligibility criteria.

Period 1:

- Participants will be admitted to the clinical research unit on Day -1 and will remain in-house until collection of the final PK sample on Day 6.
- On Day 1, participants will receive a single dose of 100 mcg nemiralisib.

Period 2:

- There will be a washout of at least 14 days between the administration of nemralisib in Period 1 and the administration of nemralisib in Period 2.
- Participants will be admitted to the clinical research unit on Day -1 and will remain in-house until collection of the final PK sample on Day 11.
- From Day 1 to 10 inclusive, participants will receive a single dose of 200 mg itraconazole in the morning.
- On Day 5, participants will receive a single dose of 100 mcg nemralisib one hour after the dose of 200 mg itraconazole.
- Participants will receive the administration of nemralisib on Day 5 and itraconazole doses on Day 5 to Day 10 only if there are no findings that are considered clinically significant by the Investigator (in consultation with the medical monitor if needed) during review of Day 4 clinical chemistry and ECG.
- Itraconazole will be administered at approximately the same time every day and approximately 1 h after a standard breakfast.
- Nemralisib will be administered at approximately the same time in Period 1 and in Period 2.

Follow-up:

Participants will be instructed to return for a follow-up visit 5-10 days after the last dose of itraconazole.

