
The typical adult dose of itraconazole is 200 mg for up to 12 weeks although intermittent usage can be up to 400 mg/day. Itraconazole dosing of 200 mg once daily for 5 days prior to the concomitant victim (nemirisib) dose will enable the victim interaction to be observed on a background of steady state exposure and similar to that seen in clinical practise [Ke, 2014]. A more recent publication describing the best practices around the use of itraconazole as a potent CYP3A4 inhibitor in DDI studies recommends at least a 3

day lead-in with co-administration of the victim compound on Day 4 [Liu, 2016]. Maximum inhibition was also seen if the victim drug was given one hour after itraconazole administration [Ke, 2014]. Itraconazole administration will continue after the dose of nemralisib to ensure that inhibition is maintained throughout the elimination phase of nemralisib.

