### **7.3. Method of Treatment Assignment**

All participants will receive the same treatments in the periods/days specified in Section 5.1.

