## 9. STUDY ASSESSMENTS AND PROCEDURES

- Study procedures and their timing are summarized in the SoA.
- Protocol waivers or exemptions are not allowed
- Immediate safety concerns should be discussed with the sponsor immediately upon occurrence or awareness to determine if the participant should continue or discontinue study treatment.
- Adherence to the study design requirements, including those specified in the SoA, is essential and required for study conduct.
- All screening evaluations must be completed and reviewed to confirm that potential participants meet all eligibility criteria. The investigator will maintain a screening log to record details of all participants screened and to confirm eligibility or record reasons for screening failure, as applicable.
- Procedures conducted as part of the participant's routine clinical management (eg, blood count) and obtained before signing of ICF may be utilized for screening or baseline purposes provided the procedure met the protocol-specified criteria and was performed within the time frame defined in the SoA.
- The maximum amount of blood collected from each participant over the duration of the study, including any extra assessments that may be required, will not exceed 500 mL
- Repeat or unscheduled samples may be taken for safety reasons or for technical issues with the samples.
- If assessments are scheduled for the same nominal time, then the assessments should occur in the following order:

1. 12-lead ECG
2. vital signs
3. blood draws.

Note: The timing of the assessments should allow the blood draw to occur at the exact nominal time.

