2.3. Study Design

Overview of Study Design and Key Features	
Design Features	
 One sequence crossover, open label, single centre. There will be a washout of at least 14 days between the administration of nemiralisib in Period 1 and the administration of nemiralisib in Period 2. Subjects will be admitted to the clinical research unit on Day -1 and will remain in-house until collection of the final PK sample in each period. The final PK sample will be Day 6 in Period 1 and Day 11 in Period 2.
Dosing	
 Period 1, nemiralisib: On Day 1, subjects will receive a single dose of 100 mcg nemiralisib. Period 2, itraconazole: From Day 1 to 10 inclusive, subjects will receive a single dose of 200 mg itraconazole in the morning Period 2, nemiralisib: On Day 5, subjects will receive a single dose of 100 mcg nemiralisib one hour after the dose of 200 mg itraconazole. Participants will receive the administration of nemiralisib on Day 5 and itraconazole doses on Day 5 to Day 10 only if there are no findings that are considered clinically significant by the Investigator (in consultation with the medical monitor if needed) during review of Day 4 clinical chemistry and ECG.
Time & Events	
 Refer to Appendix 1: Schedule of Activities.
Treatment Assignment	
 All subjects will receive the same treatments in the same periods/on the same study days.
Interim Analysis	
 A preliminary assessment of PK will be performed following the availability of the PK data, for internal decision making.

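### The Period 2 schedule of activities marks itraconazole on Days 1 to 9 only, while the protocol and SAP text require it on Days 1 to 10

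*Protocol*

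**What the plan says.** The text is consistent. The synopsis and Protocol 5.1 both say: "From Day 1 to 10 inclusive, participants will receive a single dose of 200 mg itraconazole in the morning". A further bullet in 5.1, on the Day 4 safety review, allows "itraconazole doses on Day 5 to Day 10 only if there are no findings" of clinical significance, so Day 10 is named twice in that section. SAP 2.3 repeats it: "From Day 1 to 10 inclusive, subjects will receive a single dose of 200 mg itraconazole in the morning". Protocol 7.3 points to the same place for the dosing days: "All participants will receive the same treatments in the periods/days specified in Section 5.1".

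The schedule differs. In Protocol section 2, Table 3, the itraconazole row (the one with the note "Approx. 1 h post standard meal") is marked on Days 1 to 9, and the cells for Days 10 and 11 are empty. SAP 11.1.1 reproduces the table with the same nine marks.

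Protocol 5.5 gives the reason for dosing beyond Day 5: "Itraconazole administration will continue after the dose of nemralisib to ensure that inhibition is maintained throughout the elimination phase of nemralisib". Nemiralisib is sampled to 144 h after the Day 5 dose, which is Day 11.

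**The concern.** The schedule of activities is the page a clinical unit works from, and Protocol section 9 gives it force: "Adherence to the study design requirements, including those specified in the SoA, is essential and required for study conduct". It disagrees with the text about whether a dose is given.

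If the table were followed, the inhibitor would be stopped a day early, just before the last point of the nemiralisib profile. Recovering CYP3A4 activity would lower the 144 h concentration and steepen the fitted λz. AUC(0-∞) adds C(t)/λz to AUC(0-t), so both changes shrink the extrapolated part, and they do so only in Period 2. The estimated interaction would be too small. That is the unsafe direction for a study whose results are to inform concomitant-medication criteria and possible dose modification. AUC(0-∞) is one of the two parameters modelled formally in SAP 7.1.5.1.

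**Working it through.** **1. The row against the text.** Table 3 has 12 day columns (-1, then 1 to 11).

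| Row of Table 3 | Days marked |
|---|---|
| Itraconazole dose | 1, 2, 3, 4, 5, 6, 7, 8, 9 |
| Nemiralisib dose | 5 |
| 12-lead ECG | 1, 2, 4, 6, 8, 10 |
| Full laboratory tests | -1, 10 |
| Nemiralisib PK | 5 to 11 |

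The other rows fall where the text puts them, so the columns are aligned. The itraconazole row gives 9 doses; the text gives 10.

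**2. Which one is intended.** The ECG row is marked on Day 10, and its note reads "Pre-dose at all other timepoints, Day 4 results to be reviewed before itraconazole dosing on Day 5". The laboratory and vital-signs rows are also marked on Day 10 and labelled pre-dose. The only dose these can precede is itraconazole on Day 10. Table 3 therefore contradicts itself as well as the text. The SAP table is a copy and adds no independent evidence.

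**3. Timing.** Put nemiralisib at 0 h on Day 5, one hour after itraconazole. Itraconazole on Day d is then at 24(d - 5) - 1 h.

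| | Table (last dose Day 9) | Text (last dose Day 10) |
|---|---|---|
| Total dose | 9 × 200 = 1800 mg | 10 × 200 = 2000 mg |
| Last dose | 95 h | 119 h |
| Gap to 120 h sample | 25 h | 1 h |
| Gap to 144 h sample | 49 h | 25 h |
| Follow-up (5 to 10 days later) | Days 14-19 | Days 15-20 |

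**4. Effect if Day 10 is omitted in everyone.** From Protocol 5.5: half-life 40 h, so k = ln 2/40 = 0.01733 per h; Cmax 410 pg/mL; AUC24 1200 pg·h/mL; biexponential decline. Assumed, because the documents do not give them:
- terminal intercept B of 40 or 60 pg/mL;
- fraction fm of clearance through CYP3A4;
- inhibition I constant to 24 h after the last itraconazole dose, then decaying with a half-life of 12, 24 or 36 h.

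Clearance follows k(t) = k[(1 - fm) + fm/(1 + I)]. AUC is by log-down trapezoid at the scheduled times, with λz from the last 3 or 4 samples.

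One corner in full (clearance halved, fm = 1, inhibition half-life 12 h, B = 40, three-point λz):
- With Day 10: C(96) = 17.41 and C(144) = 11.49 pg/mL. λz = ln(17.41/11.49)/48 = 0.00867. AUC(0-t) = 3740, extrapolated 11.49/0.00867 ≈ 1325, total about 5065 pg·h/mL.
- Without Day 10: C(144) = 10.69. λz = ln(17.41/10.69)/48 = 0.01017. AUC(0-t) = 3729, extrapolated 10.69/0.01017 ≈ 1051, total about 4780.
- Change: 4780/5065 - 1 = -5.6%.

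Full ranges, without against with the Day 10 dose:

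| Terminal clearance | fm | AUC(0-∞) |
|---|---|---|
| Halved | 0.6 | -0.6 to -3.2% |
| | 0.8 | -1.3 to -5.3% |
| | 1 | -1.7 to -6.1% |
| Reduced five-fold | 0.85 | -1.5 to -8.6% |
| | 0.9 | -2.7 to -13.7% |
| | 1 | -4.6 to -19.5% |

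With clearance halved, C(144) falls by 1.0 to 7.0%, C(120) by at most about 0.01%, and AUC(0-t) by at most 0.32%. With the dose given, the extrapolated share is 26 to 29% when clearance is halved and 58 to 61% when it is reduced five-fold. Period 1 is untouched, so the change in AUC(0-∞) is also the change in the ratio.

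**5. Against the planned precision.** With the protocol's within-subject SD of 0.330 and 16 participants, SE = 0.330 × √(2/16) = 0.1167. With t(15, 0.95) = 1.753, the 90% limits are exp(±0.2045) = 0.815 and 1.227 times the estimate, close to the 0.82 and 1.22 in Protocol 10.1. A 6.1% understatement is -ln(0.939)/0.1167 = 0.0629/0.1167 = 0.54 SE; 0.6% is about 0.05 SE. By the noncentral t distribution, the chance that the upper 90% limit falls below the true ratio rises from 5% to 5.5% (0.6% bias) or 12.9% (6.1% bias).

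**The case against.** The strongest reply is that the protocol already settles the matter. Section 7.3 names 5.1 as the source of the dosing days, 5.1 is unambiguous, and section 9 does not rank the schedule above it. The pre-dose labels would alert anyone reading the table alone. The study has one centre, participants are resident until Day 11, and 7.6 requires supervised, recorded doses confirmed by a second staff member. Harm needs the unit to follow the table regardless, and nothing shows how likely that is. All of this stands. It is why the intended schedule can be recovered and why the bias is only conditional. It does not remove the contradiction: confirmation by a second person does not help if both work from the same table, and the exposure record (SAP Listing 12, 1800 mg instead of 2000 mg) reveals an omission only once the dose can no longer be given on time.

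A second reply concerns the evidence. The tables were read from text extracted from the PDF, and the continuation of Table 3 has lost its Day 11 column. A full count of cells shows that no column was dropped in the first half; it cannot show that no mark was. The aligned neighbouring rows and the identical SAP copy make a real omission the likelier reading, but the cell should be checked in the source file.

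A third concerns size. The 6.1% figure is the extreme of the assumed range. With an inhibition half-life of 24 h, clearance halved and B = 40, the understatement is about 1.0 to 3.2%, roughly 0.1 to 0.3 SE. The five-fold figures arise where most of AUC(0-∞) is extrapolated even with the dose, and SAP section 9 already foresees population PK or PBPK modelling there. They should not drive the severity. No formal hypothesis is tested.

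**Conclusion.** The point holds. Table 3 omits the Day 10 itraconazole dose that the synopsis, Protocol 5.1 and SAP 2.3 require, and its own pre-dose labels show that the blank cell is the error. The statistical consequence is zero if Day 10 is dosed. If it is omitted in all participants and terminal clearance is halved (a true ratio of about 2), the AUC(0-∞) ratio is understated by about 0.6 to 6.1%, or 0.05 to 0.54 of the planned SE. AUC(0-t) barely moves and Cmax does not. The range depends on the assumed inhibition half-life, CYP3A4 fraction and terminal intercept. This should be corrected because it concerns whether a dose is given. It does not threaten the design.

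**What to change.** Add the Day 10 mark to the itraconazole row of Table 3 in Protocol section 2 and in SAP 11.1.1, after checking the cell in the source files. Both then agree with the synopsis, 5.1, SAP 2.3 and the Day 10 pre-dose assessments. The cost is one table cell in each document. No further sampling, analysis, procedures or participants are needed.
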